2.4. SOFTWARE USED

The analyses are performed using SAS[®] software (version 9.3 or higher).

3. ANALYSIS PLAN

3.1. DESCRIPTION OF THE DEVIATIONS TO THE PROTOCOL IDENTIFIED BY THE CLINICAL MONITOR/PROJECT LEADER

3.1.1. ELIGIBILITY CRITERIA ASSESSMENT

- Eligibility criteria not met (n, %)

All eligibility criteria (inclusion and non inclusion criteria) are listed below, with a description of the verification performed by the statistician, where appropriate.

- **Inclusion criteria:**

For all inclusion criteria, the statistician checks that the response to the inclusion criteria is « yes » in the corresponding SAS table. Additional verifications are listed below:

Inclusion criteria	Description of the verification performed by the statistician
1. Healthy male or female between 18 and 32 years of age, vaccinated or unvaccinated with a cellular pertussis vaccine.	Age calculated by subtraction of date of inclusion and date of birth.
2. Female subject of child bearing potential must be willing to ensure to use one of the following methods of contraception from 2 weeks before vaccination till one month after vaccination to avoid pregnancy during the study (e.g. complete abstinence from penile-vaginale intercourse, double barrier method, intrauterine device, approved hormonal contraception).	
3. Informed consent form (ICF) signed by the subject.	
4. Subject shall be able to attend all scheduled visits and to understand and comply with the study procedures.	

• **Non inclusion criteria:**

For all non inclusion criteria, the statistician checks that the response to the inclusion criteria is « no » in the corresponding SAS table. Additional verifications are listed below:

Non inclusion criteria	Description of the verification performed by the statistician
1. Individual with PT and /or PRN serum IgG antibodies ≥ 20 IU/ml. NOTE! One control group with PRN serum IgG antibodies ≥ 20 IU/ml and PT serum IgG antibodies < 20 IU/ml will be included.	
2. Vaccinated with the study vaccine in the Child Innovac study (EudraCT number 2010-019936-11).	
3. Pregnant or lactating women. Pregnancy not planned and to be avoided during the study by use of effective contraceptive methods.	
4. Blood pressure after resting $\geq 150/90$ mm Hg at screening.	
5. Heart rate after resting ≥ 80 bpm at screening.	
6. Respiratory rate after resting ≥ 20 /minute at screening.	
7. Unwillingness to refrain from the use of nicotine products from screening through day 28.	
8. Use of narcotic drugs and/or a history of drug/alcohol abuse within the past 2 years prior to screening.	
9. The subject has donated blood or suffered from blood loss of at least 450 ml (1 unit of blood) within 60 days prior to screening or donated plasma within 14 days prior to screening.	
10. Receipt of immunoglobulin, blood derived products, systemic corticosteroids or other immunosuppressant drugs within 90 days prior to day 0.	
11. Asthma or other chronic respiratory problems.	
12. Use of corticosteroids in the respiratory tract (e.g. nasal steroids, inhaled steroids) 30 days prior to day 0.	
13. Receipt of a vaccine within the last 30 days prior to day 0 or planned vaccination within the next 30 days after day 0.	
14. Known hypersensitivity to any component of the study vaccine.	
15. Current participation in any other clinical trial or participation (and during the whole study) in any clinical trial in the previous 3 months prior to day 0.	
16. Inability to adhere to the protocol, including plans to move from the area.	

Non inclusion criteria	Description of the verification performed by the statistician
17. Family history (first degree) of congenital or hereditary immunodeficiency.	Check if the laboratory result of “Screening of HIV, hepatitis B and C” is negative.
18. Past or present infection with HIV, hepatitis B or C.	
19. Chronic conditions requiring ongoing active medical interventions, such as diabetes mellitus or cardiovascular disease.	
20. Any autoimmune or immunodeficiency disease/condition (inherited or iatrogenic).	
21. Any medical condition which, in the opinion of the investigator, might interfere with the evaluation of the study objective or might affect the safety of the individual, e.g. evolving encephalopathy not attributable to another identifiable cause within 7 days of administration of a previous dose of any vaccine, hospitalization due to major depression or history of suicidal attempt.	
22. Abnormal laboratory values outside the limit of normal values for the screening laboratory with clinical significance at the discretion of the investigator.	
23. Person in frequent contact with children less than 1 year of age (parent, childcare worker, nurse, etc) or residence in the same household as persons with known immunodeficiency including persons on immunosuppressive treatment.	

3.1.2. MAJOR PROTOCOL DEVIATIONS

The other following deviations are described per category:

- Randomized participants who did not receive the trial intervention
- Participants who received the wrong intervention or incorrect dose
- Participants who received a forbidden concomitant intervention. The following therapies should be avoided during the first month after vaccination:
 - Antibacterial agents effective against *B pertussis*.
 - Immunoglobulin, corticosteroids for systemic use or for use in the respiratory tract (e.g. nasal steroids, inhaled steroids), other immunosuppressive agents or immunostimulating agents.
 - *Pertussis* vaccines.
 - Topical nasal therapies.

If it is necessary to give a medication or a vaccine, this shall be permitted for obvious reasons be permitted. All medications and vaccines will be documented in the case report form (CRF). The volunteer will be followed as pre-planned for adverse events. The immunological part of the study can also continue, but the results from the volunteer should be reported separately in the statistical analyses.

Deviations per participant are described.

3.2. DESCRIPTION OF ENROLMENT AND FOLLOW-UP

Participant enrolment and follow-up are described based on the study profile as defined in the CONSORT recommendations (3).

3.2.1. FLOWCHART

According to CONSORT diagram,

- Participants pre-enrolled (n)
- Pre-enrolled participants not enrolled (n)
- Reasons for non-enrolment (n, %)
- Participants enrolled (n, %)
- Participants having received the trial intervention (n, %)
- Withdrawals (n, %)
- Participants to include in the analysis (n, %)
- Participants to exclude from the analysis (n, %)
- Participants to include in the mITT analysis (n, %)

3.2.2. DESCRIPTION OF SCREENING

- Participants screened (n, %)
- Participants screened/non-enrolled (n, %)
- Reasons for screen failure (n, %)

3.2.3. DESCRIPTION OF ENROLMENT

- Participants enrolled (n, %)
- Enrolment graph (trend in the number of participants enrolled from 1st enrolment to last)
- Enrolled participants per group and randomized allocation (n, %)

3.2.4. DESCRIPTION OF FOLLOW-UP

- Expected visits for to the number of participants enrolled (n, %)
- Visits actually conducted (n, %)
- Ratio of observed/expected visits
- Cumulative follow-up duration, i.e. amount of participation time for each participant enrolled, that is the difference, in days, between the date of enrolment and the date of last contact with the trial. The cumulative follow-up duration is also presented in person-days.

3.2.5. DESCRIPTION OF WITHDRAWALS

- Participant withdrawals (before/after enrolment) (n, %)
- Reasons for withdrawal (before/after enrolment) (n, %)
- Time between randomization date and date of withdrawal
- Participant lost to follow-up (before/after enrolment) (n, %)
- Time between randomization date and date of follow-up
- Deceased participants (n, %)

3.2.6. DESCRIPTION OF PARTICIPANTS WHO DIDN'T TAKE THE TRIAL INTERVENTION

- Enrolled participants who did not take the trial intervention (i.e. vaccination) (n, %)

- o Reason for not taking the trial intervention (n, %)

3.3. PARTICIPANTS CHARACTERISTICS AT SCREENING (VISIT 1) AND ENROLMENT (D00)

The following characteristics are described (as numbers for qualitative variables) for all enrolled participants overall, per group (1, 2, 3, 4), and per group and randomized allocation (active vaccine or placebo) in groups 1, 2 and 3:

- Socio-demographic characteristics at visit 1 (screening);
- Clinical characteristics at visit 1 (screening) and visit 2 (D00);
- Biological characteristics at visit 1 (screening) and visit 2 (D00) (whenever planned in the protocol);
- Concomitant treatment characteristics visit 2 (D00).

3.3.1. SOCIO-DEMOGRAPHIC CHARACTERISTICS

- o Age (in years; and in classes)
- o Gender
- o Ethnicity

3.3.2. CLINICAL CHARACTERISTICS

- Anthropometric characteristics
 - o Height (in m)
 - o Weight (in kg)
 - o BMI (in kg/m²; in classes)
- Physical examination
 - o Oral temperature (in °C)
 - o General appearance (normal/abnormal)
 - o Heart (normal/abnormal)
 - o Respiratory (lung) (normal/abnormal)
 - o Skin (normal/abnormal)
 - o Nose/Throat (normal/abnormal)
 - o Neurological (normal/abnormal)
 - o Abdomen (normal/abnormal)
 - o Lymph nodes (normal/abnormal)
 - o Other (normal/abnormal)
- ECG examination
 - o ECG result (in classes: normal/abnormal, not clinical significant/abnormal, clinical significant)
- Cardiovascular characteristics

- Systolic and diastolic blood pressure (in mmHg)
- Heart rate (in bpm)
- Respiratory rate (in breath per minute)
- Medical history
- Frequency and proportion of participants presenting at least one:
 - Past medical history regardless of its nature
 - Medical history with any relevant medical findings
 - Medical history at pre-enrolment, regardless of grade and grade 3 or 4
 - History of (past or current, and separately):
 - Gastrointestinal
 - Endocrine/Metabolic
 - Cardiovascular
 - Musculoskeletal
 - Nervous
 - Respiratory
 - Eyes, ears, nose and throat
 - Skin
 - Immune/Allergic
 - Blood/Lymphatic
 - Psychiatric
 - Other

3.3.3. BIOLOGICAL CHARACTERISTICS

- Laboratory sampling (taken or not)
 - Blood sample for *pertussis* antibodies
 - Blood sample for clinical chemistry and hematology
 - Blood sample for HIV, hepatitis B and C
 - Urine safety analysis
 - Urine drug screen
 - Reason for not have been taken the sample
- Laboratory results
 - Screening of HIV (positive/negative)
 - Screening for hepatitis B (positive/negative)
 - Screening for hepatitis C (positive/negative)
 - Screening for anti-PT *pertussis* IgG antibodies in serum (in classes : < 20 IU/ml; ≥ 20 IU/ml)
 - Screening for anti-pertactin *pertussis* IgG antibodies in serum (in classes : < 20 IU/ml; ≥ 20 IU/ml)
- Urine analysis (in classes: normal/abnormal, not clinical significant/abnormal, clinical significant)

- U-Erythrocytes
- U-Leucocytes
- U-Protein
- U-Glucose
- U-Ketones
- U-Nitrites
- U-pH

- Drug screen (negative or positive)
 - Cocaine
 - Amphetamine
 - Methylene dioxymeth-amphetamine
 - Morphine
 - Benzodiazepines
 - Cannabis

- Hematology and blood chemistry (in classes: normal/abnormal, not clinical significant/abnormal, clinical significant)
 - Hemoglobin
 - RBC
 - WBC
 - Neutrophil
 - Lymphocyte
 - Monocyte
 - Eosinophil
 - Basophil
 - Platelets
 - Potassium
 - Calcium
 - Sodium
 - Creatinin
 - Albumin
 - Bilirubin
 - Alkaline phosphatase
 - Alanine amino transferase
 - Glutamytransferase
 - C-reactive protein
 - Blood glucose
 - Thyroidea stim. hormone

3.4. POOLING OF PARTICIPANTS ALLOCATED TO PLACEBO IN GROUPS 1, 2 AND 3

The description of the following characteristics will be used to assess whether participants allocated to placebo are described in groups 1, 2 and 3 can be pooled in the analysis:

- Age at screening (in years),
- Sex,
- BMI at D00 (in kg/m²),
- Occurrence of cough during follow-up in placebo recipients,
- IgG and IgA antibody titers in placebo recipients at 14 and 28 days to the following antigens:
 - PT
 - FHA
 - PRN
 - Fimbriae 2/3

Pooling of placebo recipients for all following analyses will be done if no clinically significant differences between groups (corresponding to different calendar enrolment periods) are observed.

3.5. DESCRIPTION OF SAFETY ASSESSMENTS DURING FOLLOW-UP

3.5.1. HEMATOLOGY

By group, randomized allocation and visit (pre/post vaccination – measured at visits 2, 4, 6, 8, 9 and 10):

- Hemoglobin
- RBC
- WBC
- Platelets

Intra-group comparisons may be made with appropriate tests for repeated quantitative measurements.

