
I.4. PROCEDURAL FLOW-CHART

Study Visit	1	2	3	4	5	6	7	8	8'	9
	1-6 weeks prior to visit 2	Day 0	Day 4±1	Day 7±1	Day 11±1	Day 14±1	Day 21±1	Day 28 -1; +7	Day 45 -5; +10	Month 6±1
Administrative Requirements:										
Recruitment, Medical record number, Screen form, Information and study consent ^a	X									
Demographic information (age, gender, ethnicity)	X									
Vaccination:										
Clinical Requirements:										
Complete medical history	X									
Physical examination include vital signs ^b	X	X	X	X	X	X	X	X	X	X
Interim History/Diary (AEFI documentation, concomitant medication) ^{c,d}		X	X	X	X	X	X	X	X	X
Randomization		X								
Safety Labs:										
ECG	X									
Hematology ^e	X	X		X		X		X		X
Blood chemistry ^f	X									
Screening for HIV, hepatitis B and C ^g	X									
Serum pertussis toxin and pertactin IgG antibodies	X									
Urine analysis ^h	X	X*						X*		
Nasopharyngeal aspirate for BPZE1 culture and quantitative colony counts			X	X	X	X	X	X ⁱ	X ⁱ	
Immunogenicity Labs and Sample Archive:										
Binding pertussis serum antibodies		X		X		X	X	X		X
Binding pertussis nasopharyngeal antibodies			X	X		X	X	X		X
Nasopharyngeal cytokines			X	X	X	X	X	X		X
Lymphoproliferative response		X	X ^j			X		X		X
Cryo-preserved cells		X				X		X		X
TOTAL BLOOD VOLUME APPROXIMATELY (ML)	23	109	16 ^l	8.5		109	4.5	109		109

(a) The ICF must be signed by the subject and investigator before any study specific procedure.

(b) At Visit 1, full physical examination (e.g. inspection of tonsils, palpation of glands, auscultation of pulm, measuring height and weight) including ECG and vital signs (oral temperature, blood pressure, heart rate, respiratory rate). For the following visits, physical exam will be restricted to general appearance, heart, lung, skin, nose, throat and vital signs.

(c) Adverse events following immunization (AEFI) occurring within 2 hours post-vaccination have to be recorded at the study centre and AEFI occurring from Day 0 to Day 28 have to be recorded in the Diary. If a vaccine-related AEFI is not resolved by Day 28, it must be followed up until resolution or stabilization.

(d) Serious adverse events (SAE) occurring from Visit 1 (screening) to Visit 9 have to be recorded at the study site. If an SAE is not resolved at the last visit of the concerned subject, it must be followed up until resolution or stabilization.

(e) Hematology (haemoglobin, total and differential WBC, RBC, platelets).

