To assess the general safety and tolerability of the respiratory tract including specific adverse events such as cough/spasmodic cough during the 4-28 days after vaccination by a single ascending dose of the genetically modified *B. pertussis* strain BPZE1 in healthy adult volunteers.

Safety assessments recorded during the trial include:

- general safety, i. e. general well-being of the volunteers and any symptoms reported (or experienced) by the volunteers with onset within one month after vaccine administration.
- vital signs: blood pressure, heart rate, respiratory rate, oral temperature.
- abnormalities in the following laboratory data: haemoglobin (i.e. b-haemoglobin), total and differential white blood cell count (i.e. granulocytes: neutrophils, eosinophils, and basophils, non-granulocytes: lymphocytes and monocytes) platelets (thrombocytes) and RBC).
- specific side effects:
 - cough during the 28 days period (colonization period) after vaccination.
 - spasmodic cough, defined as rapid repetitive cough without intervening inspiration usually occurring as sudden intensified attacks of involuntary coughing (paroxysms) that may occur at different times in a way that is not regular several times per 24 hours during the 28 days period (colonization period) after vaccination.
 - other symptoms from the respiratory tract: sneezing, swollen nose, cough, bleeding from the nose, pain or other symptoms from the ear, symptoms from the eyes (redness, secretion).

IV.2. SECONDARY OBJECTIVES

To assess after vaccination by a single ascending dose of the genetically modified *B. pertussis* strain in healthy adult volunteers:

- 1) the safety and tolerability of the vaccine over 6 months post-vaccination
- 2) the frequency of colonization of the human respiratory tract by live attenuated *B. pertussis* strain and its magnitude (in terms of colony forming units) over 28-days post-vaccination.
- 3) the levels of serum IgG and IgA antibodies to 4 different *B. pertussis* antigens (pertussis toxin (PT), filamentous hemagglutinin (FHA), pertactin (PRN), and fimbriae 2/3) over 6 months after vaccination.

IV.3. EXPLORATORY OBJECTIVES

To assess the B and T cell immune responses to 4 different *B. pertussis* antigens (pertussis toxin (PT), filamentous hemagglutinin (FHA), pertactin (PRN), and fimbriae 2/3) over 6 months after vaccination by:

- 1) the levels of IgG and IgA in nasopharyngeal aspirate

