- The study may be stopped if a volunteer within the period 0-28 days after vaccination suffers from clinical whooping cough without laboratory demonstration of wild-type *B. pertussis*. In such a case it must be suspected that the symptoms are caused by BPZE1.
- The study may be stopped if a volunteer has a SAE which is considered by the DSMB to be most probably caused by BPZE1.

At the regular DSMB meetings before the start of dose group 2 and 3, respectively, the DSMB will review all accumulated safety data in the trial (AEs and SAEs per dose and randomized allocation) and make a recommendation whether the next higher dose can be administered.

A DSMB charter will describe the functioning of the DSMB.

XIV. Endpoints

XIV.1. PRIMARY SAFETY ENDPOINT

The primary safety endpoint will be the number and proportion of participants, per dose group and randomized allocation, with at least one of the following adverse events between Day 0 (Visit 2) and Day 28 (Visit 8):

- Cough and spasmodic cough of grade 2 or higher.
- Other respiratory tract AE related or possibly related to vaccination of grade 3 or higher.
- Any other AE related or possibly related to vaccination of grade 3 or higher.

XIV.2. SECONDARY SAFETY ENDPOINT

The second safety endpoint will be the number and proportion of participants per dose group and randomized allocation, with:

- at least one episode of cough or spasmodic cough, described by grade, between Day 4 and Day 28
- at least one solicited or unsolicited AEFI from respiratory tract between Day 0 and Day 28
- at least one AEFI with difficulties in breathing (asthma, spasmodic cough, pneumonia) between Day 0 and Day 28
- at least one other AEFI from the respiratory tract between Day 0 and Day 28
- at least one episode of cough, described by grade, between Day 0 and Day 28
- at least one episode of spasmodic cough, described by grade, between Day 0 and Day 28
- at least one solicited systemic AEFI between Day 0 and Day 28 (fever, headache, tiredness)
- at least one unsolicited AEFI between Day 0 and Day 28

Adverse events following immunization (AEFI) should be reported at study visits during the first 28 days of the concerned subject.

Serious adverse events (SAE) should be reported immediately but no later than 24 hours after detection. AEFI which lead to difficulties in breathing (asthma, spasmodic cough, pneumonia) will be considered as serious and reported to the Data Safety Monitoring Board (DSMB) and the sponsor.

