Qualitative variables will be described in terms of number, proportion and exact binomial confidence interval of proportion.

Intra-group comparisons will be made using McNemar test or other, depending on the number of modalities of the variables of interest.

Titers

Geometric means and their 95% confidence interval will be calculated for titers.

XV.2.2 Analysis software

Analyses will be performed using SAS® software (version 9.3 or higher) and R software.

XV.2.3 Analysis plan

A detailed statistical analysis plan will be established before the first statistical analyses of the trial.

Descriptive statistics will be provided for demographic and other baseline characteristics.

Hematology

Pre- and post-vaccination values of cell blood counts (haemoglobin, total and differential WBC, RBC and platelets) will be described for each group separately. Within group comparisons may be done using appropriate tests for paired measurements.

Primary Safety endpoint

The primary endpoint will be described per group and randomized allocation, in modified ITT population, with participants with missing follow-up data considered event-free in primary analysis. Numbers, percentages and 95% confidence intervals will be shown. Each individual component of the primary endpoint will also be described.

Secondary endpoints

Secondary endpoints will be described per group and randomized allocation, displaying numbers, percentages and 95% confidence intervals (qualitative variables); medians and interquartile intervals (quantitative variables) or geometric mean and 95% confidence interval (antibody titers).

Number, time of occurrence and duration of secondary safety endpoints will be described.

Colonization endpoints will be described (number and proportion of participants with colonization at each post-vaccination visit; number of visits during which bacteria are detected; magnitude of bacterial colonization (number of cfu) per post-vaccination visit)

Pre- and post- vaccination serum IgG and IgA antibody endpoints will be described per group and randomized allocation. Within group comparisons may be done using appropriate tests for paired measurements.

Cough, spasmodic cough and any symptom from the respiratory tract, as well as antibody titers, will be described for each of the vaccine groups and the pooled placebo group, and for the groups of colonized and non-colonized individuals.

Exploratory endpoints

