3.10. INTERIM REPORTS FOR DSMB

Overall, per group and randomized allocation, and by period (pre/post vaccination):

- Number and proportion of participants with at least :
 - one AEFI during available follow-up
 - one AR during available follow-up
 - one SAE during available follow-up
 - one work accident
- Number of following AEs during available follow-up:
 - Solicited or unsolicited adverse reaction from respiratory tract
 - AEFI with difficulties in breathing (asthma, spasmodic cough, pneumonia)
 - Cough
 - spasmodic cough
 - solicited systemic adverse event
 - unsolicited adverse event

- Participants with at least one cough or spasmodic cough of grade 2 or higher between Day 0 and Day 28 (n, %)
- Participants with at least one other respiratory tract AE related or possibly related to vaccination of grade 3 or higher between Day 0 and Day 28 (n, %)
- Participants with any other AE related or possibly related to vaccination of grade 3 or higher between Day 0 and Day 28 (n, %)
- Participants with at least of the adverse events listed above (primary endpoint) (n, %, 95% CI)
- Participants with at least one solicited or unsolicited adverse reaction from respiratory tract between Day 0 and Day 28 (n, %, 95% CI)
- Participants with at least one AEFI with difficulties in breathing (asthma, spasmodic cough, pneumonia) between Day 0 and Day 28 (n, %, 95% CI)
- Participants with at least one other AEFI from the respiratory tract between Day 0 and Day 28 (n, %, 95% CI)
- Participants with at least one cough between Day 0 and Day 28 (n, %, 95% CI)
 - duration of symptoms (mean, median, SD, IQR, 95% CI)
- Participants with at least one spasmodic cough between Day 0 and Day 28 (n, %, 95% CI)
 - duration of symptoms (mean, median, SD, IQR, 95% CI)
- Participants with at least one solicited systemic adverse events between Day 0 and Day 28 (fever, headache, tiredness) (n, %, 95% CI)
- Participants with at least one unsolicited adverse event between Day 0 and Day 28 (n, %, 95% CI)

Detailed listings of individual events will be provided in an appendix of the reports.

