3.11. CONFIDENTIAL INTERIM ANALYSIS FOR DECISION MAKING FOR PHASE II DESIGN

An interim analysis will be performed when culture results are available from twenty-eight days after vaccination of the high dose group 3. The interim analysis will provide summary data only (i.e. no information about individual volunteers) for the sponsor/ILiAD to present to regulatory agencies, partners, and funding sources to aide in designing and planning a Phase II study.

Descriptive statistics will be provided for demographic and other baseline characteristics.

COLONIZATION

The frequency of colonization of the human respiratory tract by live attenuated B. pertussis strain (BPZE1) and its magnitude (in terms of colony forming units, CFUs) will be summarized for each group. Descriptive statistics for the CFUs, including the mean, standard deviation, minimum, maximum, median, and 95% confidence intervals will be constructed and reported.

SYMPTOMS FROM THE RESPIRATORY TRACT

Cough, spasmodic cough and any symptom from the respiratory tract will be summarized using counts and percents for each of the vaccine groups and between the groups of colonized and non-colonized individuals.

HEMATOLOGY

Pre- and post-vaccination values of cell blood counts (haemoglobin, total and differential WBC, RBC and platelets) will be summarized for each group separately. Descriptive statistics, n, mean, standard deviation, minimum, maximum, median, and 95% confidence intervals will be constructed and reported.

REFERENCES

1. Guideline ICH - E9: Statistical Principles for Clinical Trials. 1998.
2. Guideline ICH - E3: Statistical Principles for Clinical Trials. 1995.
5. Basic Statistical Reporting for Articles Published in Biomedical Journals: The « Statistical Analyses and Methods in the Published Literature » or The SAMPL Guidelines” | The EQUATOR Network [Internet]. [cité 9 mai 2014]. Disponible sur: <http://www.equator-network.org/reporting-guidelines/sampl/>

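### SAP 3.5.1 leaves out the follow-up differential white-cell counts that protocol XV.2.3 says will be described

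*Combined protocol and SAP*

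**What the plan says.** Protocol IV.1 (primary objective) includes among the recorded safety assessments "abnormalities in the following laboratory data: haemoglobin (i.e. b-haemoglobin), total and differential white blood cell count", and names the five cell types. The flow-chart in protocol I.4 schedules haematology at Visits 1, 2, 4, 6, 8 and 9, and its footnote defines the test as "Hematology (haemoglobin, total and differential WBC, RBC, platelets"). The analysis commitment in protocol XV.2.3 reads: "Pre- and post-vaccination values of cell blood counts (haemoglobin, total and differential WBC, RBC and platelets) will be described for each group separately".

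The SAP treats the differential in four different ways:

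- **3.3.3 (screening and Day 0):** WBC and each of the five cell types are separate items under "Hematology and blood chemistry (in classes: normal/abnormal, not clinical significant/abnormal, clinical significant").
- **3.5.1 (follow-up, final analysis):** values by group, allocation and visit, "measured at visits 2, 4, 6, 8, 9 and 10". The list is haemoglobin, RBC, WBC and platelets.
- **3.10 (DSMB reports):** AE, AR, SAE and symptom summaries with no haematology table. It adds: "Detailed listings of individual events will be provided in an appendix of the reports".
- **3.11 (interim for phase II planning):** "Pre- and post-vaccination values of cell blood counts (haemoglobin, total and differential WBC, RBC and platelets) will be summarized for each group separately".

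On dose escalation, protocol XIII.7 says "the DSMB will review all accumulated safety data in the trial". The same sentence then specifies those data, in brackets, as AEs and SAEs by dose and randomized allocation.

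**The concern.** A safety measure that is collected, named under the primary objective and promised in the protocol's analysis section drops out of the SAP section that produces the final follow-up tables. No reason is given. The interim written for phase II planning would then contain a safety summary that the trial's own final analysis lacks.

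Total WBC is not a substitute. It can stay level while cell types move in opposite directions. With assumed values for illustration, lymphocytes rising from 2.0 to 3.5 and neutrophils falling from 4.0 to 2.5 (x10^9/L), other cells unchanged, leave their sum at 6.0 both times. Nothing in the documents suggests that such a shift is expected. The example shows only why a total does not stand in for its components.

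A related but lesser matter is escalation. Site staff judge laboratory values one participant at a time, blinded to allocation (protocol II.3 and XI.4). A modest shift across the active arm, with no single value judged clinically significant, would show only in a table by arm. The DSMB reports are unblinded and could hold such a table, but SAP 3.10 does not list one.

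**Working it through.** The point rests on no power, alpha or sample-size figure, so there is no plan figure to reproduce. The check compares the texts and counts what is affected.

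**1. Parameters.** Protocol XV.2.3 with IV.1: haemoglobin, RBC, total WBC, platelets and five cell types = 9. SAP 3.5.1: 4. Missing: 9 − 4 = 5, exactly the differential.

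**2. Could WBC in 3.5.1 include the differential?** Not safely. SAP 3.3.3 lists WBC and the five cell types as separate items, and SAP 3.11 names total and differential WBC explicitly when it means both.

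**3. Planned post-vaccination samples under 3.5.1.** Inputs: 48 participants in groups 1 to 3 and 6 in group 4, so 54. Visits 4, 6, 8 and 9 apply to all. Visit 10 is taken as the 12-month visit, which the SAP objectives confine to groups 1 to 3.

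- Visits 4, 6, 8, 9: 54 × 4 = 216
- Visit 10: 48 × 1 = 48
- Total: 216 + 48 = 264

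The protocol's schedule ends at Visit 9, so it is an assumption that the Visit 10 sample includes a differential. Without Visit 10 the total is 216.

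**4. What SAP 3.11 covers.** SAP 2 and 2.1.6 limit it to groups 1 to 3 up to Day 28 (Visits 4, 6, 8): 48 × 3 = 144 samples, summarised by group with no stated split by allocation. Samples with no planned differential summary anywhere:

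- Group 4, Visits 4, 6, 8: 6 × 3 = 18
- Visit 9, all groups: 54
- Visit 10, groups 1 to 3: 48
- Sum: 18 + 54 + 48 = 120, which equals 264 − 144. Without Visit 10 it is 72.

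SAP 1.4 mentions group 4 in the timing of this interim. If group 4 were included to Day 28, coverage would be 54 × 3 = 162 and the remainder 264 − 162 = 102 (54 without Visit 10).

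**5. Timing and audience of 3.11.** It runs once Day 28 cultures from group 3 are available, which is after both escalations. SAP 2.1.6 withholds it from those executing the study until data lock. It cannot inform escalation.

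**6. DSMB reports.** Each is due when the cohort reaches Day 28, so Visits 4, 6 and 8 will have taken place. Post-dose samples available: up to 16 × 3 = 48 before group 2, and up to 32 × 3 = 96 cumulatively before group 3. Haematology tables listed in SAP 3.10: none.

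**The case against.** The strongest reply is that these counts are looked at. A reader might infer from the SAP's silence that the differential goes unreviewed; the documents do not support that. Under protocol XI.1 haematology results go into the eCRF. Under XI.4 the investigator or a delegate evaluates every laboratory abnormality and reports those that are clinically significant. An abnormal laboratory finding can be an AEFI (XIII.1), biological adverse events go on the AE form (XIII.3), and from there they enter the DSMB counts and event listings. SAP 3.11 also tabulates the differential. All of this stands. What is missing is the group-level follow-up summary in the final analysis.

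A reader might also infer that SAP 3.10 breaks a protocol promise to give the board all safety data. It does not. Read to its end, the sentence in XIII.7 defines those data as AEs and SAEs, which SAP 3.10 supplies. The DSMB charter, which may say more, is not among the documents.

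Nor is haematology a named component of the primary endpoint. It counts there only through a related or possibly related AE of grade 3 or higher.

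Finally, SAP 3.5.1 does not say that its list is exclusive, and the SAP presents itself as a more detailed account of the protocol's analysis, so the commitment in XV.2.3 arguably still stands. That is fair. But the final tables are specified from the SAP, and where its list is shorter than the protocol's the two need reconciling.

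**Conclusion.** The omission in SAP 3.5.1 is a clear mismatch with protocol XV.2.3 and should be corrected. Its size is five of nine haematology parameters at every follow-up visit of the final analysis, or up to 264 planned samples. For 120 of these no section of the SAP plans a differential summary; for the other 144 the only one is an interim by group, without a stated split by arm. These counts assume full enrolment and attendance and a differential at Visit 10. The mismatch itself depends on none of them.

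The lack of a haematology table in SAP 3.10 is a weakness, not a breach. Its consequence is limited to group-level shifts in which no single value was judged clinically significant. The documents give no evidence that such a shift is likely. No sample size, power or error rate changes.

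**What to change.** **Needed.** Add neutrophils, lymphocytes, monocytes, eosinophils and basophils to the list in SAP 3.5.1, by group, randomized allocation and visit, using the quantitative summaries already set out in SAP 2.2.1. State whether the Visit 10 sample includes a differential.

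**Recommended, separately.** Add to SAP 3.10 a descriptive haematology table for Visits 2, 4, 6 and 8 by randomized allocation, including the differential. If the sponsor prefers not to, SAP 3.10 should say that laboratory findings reach the board only as adverse events.

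**Optional.** Change from Day 0 (SAP 2.3.2 already defines the difference), counts outside the normal range, and a shift listing. The protocol asks only that values be described.

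**Cost.** SAP wording, five more rows in a planned table and one further DSMB table. Haematology results are already entered in the eCRF provided by EUCLID, which also prepares the DSMB reports and the final analysis. No new samples are needed for visits up to Visit 9. The change to 3.5.1 is useful at any time before the final analysis; the DSMB table helps only with escalations still to come when the SAP is amended.
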